## 14.0 Sample Size Considerations

This is primarily a (structured) exploratory study to discover patterns of cell kinetics in CLL. There are no data from previous experiments that would permit specification of a formal alternative hypothesis for which a power or precision calculation could be made. The proposed sample size is 30 subjects of which it is expected that 18 (approximately 60%) will be evaluable. An evaluable patient for the purpose of this protocol is primarily defined as a patient who has been able to adhere to all protocol-required procedures and blood draws during the heavy water labeling period, the resting period, and during treatment with PCI-32765. In addition, to be considered an evaluable patients, sufficient material with detectable levels of heavy water-labeled CLL cells must be recovered from the blood specimen by our colleagues at the Feinstein Institute and at KineMed, Inc. Specifically, it is expected that about 20% of subjects will exhibit a delayed release of labeled cells into the circulation in Period 1, which will manifest itself as an initially “flat” response; this number is based on available information from previous studies of this type. These subjects will be excluded from both the Period 1 and 2 analyses, but may be analyzed separately. In addition, it is anticipated that 20% of subjects will not be able to delay treatment for the desired 12-16 weeks post-labeling. These subjects will also be excluded from both the Period 1 and 2 analyses, but their data may be analyzed and used separately. The proposed sample size is consistent with other studies in CLL using similar methodologies. If necessary, the overall accrual will be increased in order to yield at least 20 evaluable subjects.

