### **8.3 Treatment with PCI-32765**

PCI-32765 will be administered with 8 ounces (~240mL) of water at a dose of 420 mg (3 x 140mg capsules) orally once daily and will be continued daily. A PCI-32765 dose of 420 MG PO once daily is based on the experience in Phase 1 and Phase 2 trials which established this dose and schedule to be adequate to induce BTK target occupancy (see

Advani et al, JCO 2012). 420 mg is the dose used in all of the CLL/SLL trials to date. Each dose of PCI-32765 should be taken at least 30 minutes before eating and at least 2 hours after a meal at approximately the same time each day. Subjects will be instructed to avoid grapefruit juice due to CYP450 3A4 inhibition. Compliance with PCI-32765 ingestion will be documented using a diary. Treatment duration will be 12 cycles, with each cycle consisting of 28 days. Response will be evaluated after 3, 6 and 12 cycles. It will be possible for subjects to continue taking the drug beyond 12 cycles if there is a significant benefit such as an ongoing PR or CR. Unused PCI-32765 will be returned for disposal per institutional policy.

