### **8.9 Sample Collections for H-DNA-labeled Leukemic Cells during PCI-32765 Treatment Phase**

After beginning PCI-32765 therapy, subjects will be seen for follow-up visits including blood draws (60ml) at day 1 (+/- 3 days), day 3 (+/- 1 day), week 2 (+/- 3 days), and every 2 weeks (+/- 3 days) thereafter for a period at least equal in duration to that of the initial H2O washout phase of 6 to 12 weeks. At these visits, clinical and laboratory assessment, which will include blood sampling (60ml) for H2O kinetic measurements, will be made. Subjects will continue to return or be seen by a local physician or clinical laboratory each month (+/- 3 days) for an additional 3 months for blood drawing (60ml). Data obtained from these blood samples will permit a determination of the slope and rate of the appearance of previously labeled CLL cells in the blood, and the slope and rate of the disappearance of labeled cells from the blood. If re-circulation to solid tissues is inhibited by PCI-32765 therapy, the disappearance rate will represent primarily the death rate of leukemic cells *in vivo*. Because during the treatment period, H2O will not be available to label newly-born cells, any cells containing H-labeled DNA will represent cells labeled during the initial period of H2O consumption and retained *in situ*. The kinetic measurements of the entire CLL clone will be compared with those of intracлонаl fractions from the same samples, defined by the reciprocal differences in CXCR4/CD5 surface membrane densities; this approach is described in the published study by Calissano et al. (Mol Med 2011;17: 1374-1382, 2011). In addition, these fractions will be analyzed for:

1. Phenotype and numerical changes of B and T cells and myeloid cells within these fractions, pre- and post-ibrutinib therapy
2. Gene expression profiles of cells within these fractions, pre- and post-ibrutinib therapy
3. DNA methylation profiles of cells within these fractions, pre- and post-ibrutinib therapy.

4. Response to BCR and other signals of cells within these fractions, pre- and post-ibrutinib therapy, using western blots on phosphoproteins/ibrutinib occupancy
5. Differences in engraftment and growth capacities of CLL B and T cells in NSG mice, unseparated or within these fractions, pre- and post-ibrutinib therapy

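### Read literally, Section 14.0 makes evaluability depend on complete adherence throughout PCI-32765 treatment, so a subject with a full kinetic series can be counted non-evaluable and replaced because of a later event

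*Combined protocol and SAP*

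**What the plan says.** **Section 14.0 (Sample Size Considerations).** The expectation is: "The proposed sample size is 30 subjects of which it is expected that 18 (approximately 60%) will be evaluable". Evaluability has two conditions. The first is to "adhere to all protocol-required procedures and blood draws during the heavy water labeling period, the resting period, and during treatment with PCI-32765". The second is introduced as an addition: "sufficient material with detectable levels of heavy water-labeled CLL cells must be recovered". Two expected losses follow: "about 20% of subjects will exhibit a delayed release of labeled cells into the circulation in Period 1", and another 20% who cannot postpone treatment long enough. Both groups are expressly left out of the Period 1 and Period 2 analyses, with separate analysis allowed. The section closes: "If necessary, the overall accrual will be increased in order to yield at least 20 evaluable subjects".

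**Timing.** Section 8.3: "Treatment duration will be 12 cycles, with each cycle consisting of 28 days". Section 8.9 has kinetic draws at days 1 and 3 of treatment, then two-weekly for at least as long as the 6-to-12-week washout, then "each month (+/- 3 days) for an additional 3 months for blood drawing (60ml". Section 8.2 also mentions monthly draws but gives no end. Sections 7.0 and 10.0 require marrow aspiration and CT after cycle 12.

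**Other criteria for a usable subject.** Section 8.2 admits subjects to the kinetic studies by weeks off heavy water (at least 6, or fewer with the investigator's approval). Section 13.0, at its interim looks, asks whether enough kinetic data were obtained after 3 months of treatment. Section 13.0 also fits curves subject by subject and plans no formal inference.

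**The concern.** The measurement of interest is a labelled-cell curve that is finished well before treatment is. The evaluability rule is not limited to the samples behind that curve: it covers every procedure and draw until treatment ends. A subject with a complete kinetic series could be reclassified by something that happens months later, such as stopping the drug in cycle 8 or missing the cycle 12 marrow. A single missed two-weekly draw has the same effect, although a per-subject curve could still be fitted to the remaining draws.

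Two things are at stake. Usable series may be set aside in a 30-subject study. And because extra accrual is counted in evaluable subjects, those set aside would be replaced by subjects who stayed on schedule, so the described patterns could depend on post-treatment events. Describing patterns is the main product of this study, so an undefined analysed set matters even without hypothesis tests.

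**Working it through.** **1. The plan's own figure.** Inputs from Section 14.0: 30 enrolled, 20% delayed release, 20% unable to delay.

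30 x (1 - 0.20 - 0.20) = 18.0, which matches the stated 18 and 60% exactly.

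If the two losses were independent and could overlap, 30 x 0.80 x 0.80 = 19.2, leaving a margin of 19.2 - 18 = 1.2 subjects. The stated percentage fits the additive version, which leaves no margin.

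**2. When kinetic sampling ends and when the rule ends** (Sections 8.3 and 8.9, taking 3 months as 12 weeks).

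- Last kinetic draw: 6 + 12 = 18 weeks with a 6-week washout; 12 + 12 = 24 weeks with a 12-week washout.
- Treatment: 12 x 28 = 336 days = 48 weeks, with marrow and CT due after cycle 12.
- Gap: 48 - 24 = 24 weeks to 48 - 18 = 30 weeks, in which the kinetic series is complete but the rule still applies.

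These end points follow Section 8.9. If the open-ended monthly draws in Section 8.2 were also required, there would be more draws and a later end.

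**3. Number of kinetic draws that must all be present** (Sections 8.1, 8.2, 8.9; baseline and day 1 of labelling counted once).

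| Washout | Labelling | Resting | Days 1 and 3 | Two-weekly | Monthly | Total |
|---|---|---|---|---|---|---|
| 6 weeks | 3 | 3 | 2 | 3 | 3 | 14 |
| 12 weeks | 3 | 6 | 2 | 6 | 3 | 20 |

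The total is one lower if the last resting draw is also the day 1 treatment draw.

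**4. Sensitivity to further loss.** The documents give no rate for missed draws or early stopping, so the share s of otherwise evaluable subjects lost is assumed. Evaluable = 18 x (1 - s). Enrolment for 20 evaluable = 20 / [0.60 x (1 - s)], rounded up.

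| s (assumed) | Evaluable of 30 | Enrolment for 20 evaluable |
|---|---|---|
| 0% | 18.0 | 34 |
| 5% | 17.1 | 36 |
| 10% | 16.2 | 38 |
| 20% | 14.4 | 42 |

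**5. How strict an every-draw rule is.** Assume each draw is obtained independently with probability p. The chance of missing none is p^14 to p^20.

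- p = 0.99: 0.869 to 0.818; times 18 gives 15.6 to 14.7.
- p = 0.95: 0.488 to 0.358; times 18 gives 8.8 to 6.5.

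This shows only how strict the wording is. It is not a forecast, and since it counts missed kinetic draws it does not measure selection on outcome.

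**6. Three criteria side by side.** Section 8.2: time off heavy water, or approval. Section 13.0: adequate kinetic data at 3 months of treatment. Section 14.0: full adherence plus detectable label. The interim thresholds (3 of 5, 6 of 10) are 60%, the same share as 18 of 30, but on a looser criterion. The interim check could therefore pass while the Section 14.0 count falls short.

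**The case against.** A reader might infer that anyone who stops early or misses a visit is removed from the analysis, and that the analysed set is therefore selected on tolerance and outcome. The documents do not support that as a stated feature:

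- Express exclusion from the Period 1 and 2 analyses covers only the delayed-release and unable-to-delay groups. No sentence drops a subject from the curve fits for a missed visit or an early stop.
- The rule requires adherence during treatment, not completion of 12 cycles. A subject who stops under the protocol's own rules and attends the end-of-study visit could be read as adherent.
- Nothing ties the comparison of kinetics with response to the evaluable set. Section 8.2 keeps subjects who fail its own kinetic criterion in the response studies.
- The definition is hedged: "An evaluable patient for the purpose of this protocol is primarily defined as a patient who has been able to adhere to all".
- Inability to delay treatment is itself partly an adherence failure, so the allowance is not wholly silent on adherence.
- The interim looks name patient compliance and would pause the study if the yield were low.

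Most of this stands and limits the claim. The hedge helps least: the next sentence adds a second condition, so adherence reads naturally as the first of two, and no tolerance is stated. The interim check uses a different criterion, so it does not protect the Section 14.0 count. That an early stop can be read either way is itself a weakness, because inclusion could be decided after the curves have been seen.

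**Conclusion.** The point holds as a defect of definition. Followed as written, Section 14.0 can count a subject with a complete kinetic series as non-evaluable, and replace that subject, because of an event in the 24 to 30 weeks after kinetic sampling ends; one missed draw has the same effect. This rests on the literal reading and on the Section 8.9 sampling schedule. Selection on tolerance or outcome is a risk of that reading, not something the plan states, and its size cannot be estimated from the documents.

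The 18 of 30 has no allowance for missed draws or on-treatment non-adherence. An assumed further loss of 5% to 20% would leave about 17 to 14. Even with no further loss, 20 evaluable subjects at 60% need 34 enrolled. With no formal inference planned, the harm is descriptive bias and lost data, not a false-positive rate. Severity: should be fixed.

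**What to change.** In Section 14.0, replace the all-procedures rule with sets defined by the data each analysis needs:

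1. **Period 1.** Baseline and labelling samples for the birth rate, plus a prespecified minimum number of resting-phase samples for the disappearance rate.
2. **Period 2 kinetics.** A sample at the start of PCI-32765 plus a prespecified minimum number of later kinetic samples, enough for the curve to be fitted. Use all available draws, whatever the later treatment status and whether or not non-kinetic procedures were missed. As a floor, a parabola (one of the curves named in Section 13.0) has three coefficients, so three points fit it exactly and a fourth is needed before misfit can show; the richer candidates need more.
3. **Kinetics versus response.** All treated subjects with a kinetic estimate, including those who stopped early.

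Count the evaluable target and any extra accrual against set 2. Report every exclusion with its reason. Reconcile the criteria in Sections 8.2, 13.0 and 14.0, and the end of monthly draws between Sections 8.2 and 8.9. Restate the 18 of 30 with its non-adherence assumption shown.

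The cost is protocol wording only, with no added visits or samples. The downside is that some individual curves will rest on fewer draws and be less precise.

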### **8.2 Heavy Water Protocol: Resting phase.**

At the end of the 4th week, subjects will stop drinking  $^2\text{H}_2\text{O}$  (washout phase) and be followed for 6-12 weeks until beginning treatment with PCI-32765. During the period until initiation of therapy, subjects will be seen every 2 weeks (+/- 3 days) for follow-up visits with clinical and laboratory assessment. Blood will be drawn at the same time every 2 weeks (+/- 3 days), to determine a disappearance rate (death plus re-distribution into solid tissue) of CLL cells containing  $^2\text{H}$ -labeled DNA. Only those subjects that have not imbibed  $^2\text{H}_2\text{O}$  for at least 6 weeks from the end of the labeling period until starting on treatment with PCI-32765 or those patients who have not imbibed heavy water for less than 6 weeks and have received study PI approval will be included in further  $^2\text{H}_2\text{O}$  kinetic studies, although they will receive PCI-32765 as a part of the response to therapy studies. After start of treatment with PCI-32765, there will be blood sampling (60ml) for CLL cell kinetic measurements (heavy water testing) on days 1 (+/- 3 days), 3 (+/- 1 day), and then at week 2 (+/- 3 days) and every 2 weeks (+/- 3 days) thereafter for a period of at least equal in duration to that of the initial  $^2\text{H}_2\text{O}$  washout phase (6 to 12 weeks). Patients will continue to return to clinic each month for blood drawing (60ml). Data obtained from these blood samples will permit a determination of CLL birth rate as well as a slope of labeled cell emergence from solid tissue into the peripheral blood.

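### Section 14 excludes subjects who cannot wait 12 to 16 weeks after labeling, but Section 8.2 schedules a 6 to 12 week rest and admits anyone with at least 6 weeks

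*Combined protocol and SAP*

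**What the plan says.** Section 14 expects 30 subjects, of whom "it is expected that 18 (approximately 60%) will be evaluable". It names two losses of about 20% each. The first is subjects with a delayed release of labeled cells, seen as a flat initial response. The second is given as "it is anticipated that 20% of subjects will not be able to delay treatment for the desired 12-16 weeks post-labeling". The next sentence turns this into an analysis rule: "These subjects will also be excluded from both the Period 1 and 2 analyses, but their data may be analyzed and used separately". Section 14 has no exception for investigator approval.

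Section 8.2 describes a different window. After four weeks of labeling, subjects are to "be followed for 6-12 weeks until beginning treatment with PCI-32765". It also has its own entry rule for the kinetic studies. Subjects qualify if they have been off heavy water "for at least 6 weeks from the end of the labeling period until starting on treatment with PCI-32765", and so do "those patients who have not imbibed heavy water for less than 6 weeks and have received study PI approval".

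The 6 to 12 week figure recurs in Section 8.9, in Section 10.0 and in footnotes k, l and q of the Schedule of Events. The heavy-water part of that schedule ends at Day 112. Only Section 14 gives 12 to 16 weeks.

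**The concern.** The plan gives two different answers to who enters the kinetic analyses, which serve the primary objective. A subject who rests 6 to just under 12 weeks follows the schedule and meets the entry rule in Section 8.2, yet Section 14, read as written, leaves that subject out of the main analyses.

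Section 14 is also at odds with itself. Its main definition of an evaluable patient is someone "able to adhere to all protocol-required procedures and blood draws during the heavy water labeling period, the resting period" and on treatment, with enough detectable labeled material recovered. An 8-week rester meets the adherence part of that definition.

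The expected evaluable number is affected too, because one of its two loss figures is measured against the unscheduled window. Section 14 adds that, if necessary, "the overall accrual will be increased in order to yield at least 20 evaluable subjects", so the rule chosen can change how many people are enrolled. The interim checks in Section 13 (3 of 5 and 6 of 10 patients with sufficient kinetic measurements) do not say which rest rule applies.

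**Working it through.** **Inputs.** Labeling lasts 4 weeks (Sections 8.1 and 13.0). Rest is 6 to 12 weeks (Section 8.2), against 12 to 16 weeks after labeling (Section 14). Enrolment is 30, with losses of 20% and 20%, 18 expected evaluable and a target of at least 20 (Section 14).

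**1. The plan's own figure.** Adding the losses gives 30 × (1 − 0.20 − 0.20) = 18, an exact match. Multiplying them gives 30 × 0.80 × 0.80 = 19.2. The plan evidently added them, and I do the same below.

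**2. The windows on one clock, from the first heavy-water dose.**

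| Source | Rest after labeling | Treatment start |
|---|---|---|
| Section 8.2 | 6 to 12 weeks | weeks 4 + 6 = 10 to 4 + 12 = 16 (day 70 to 112) |
| Section 14 | 12 to 16 weeks | weeks 4 + 12 = 16 to 4 + 16 = 20 (day 112 to 140) |

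The windows meet only at 12 weeks of rest. Section 14's window runs up to 140 − 112 = 28 days past the last scheduled heavy-water visit.

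**3. Could Section 14 have counted from the first dose?** Its text says after labeling. Counted from the first dose, it would mean 12 − 4 = 8 to 16 − 4 = 12 weeks of rest. Rests of 6 to under 8 weeks would still be admitted by Section 8.2 and excluded by Section 14.

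**4. Evaluable count under the Section 8.2 rule.** Take Section 14's 20% as the share not reaching 12 weeks of rest. Let r be the part of that share that also fails Section 8.2, by resting under 6 weeks without approval. Then r lies between 0 and 20%, and the evaluable count is 30 × (1 − 0.20 − r):

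- r = 20%: 30 × 0.60 = 18
- r = 10%: 30 × 0.70 = 21
- r = 0: 30 × 0.80 = 24

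The documents give no distribution of rest times, so r cannot be fixed. With multiplied losses the range is 19.2 to 24.

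**5. Accrual.** Enrolment needed for 20 evaluable is 20 / 0.60 = 33.3, so 34, at the planned yield. It is 20 / 0.80 = 25 if r = 0. Thirty subjects are enough if 30 × (0.80 − r) ≥ 20, that is, if r ≤ 0.80 − 20/30 = 13.3%, or 4 of 30.

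**The case against.** The strongest reply is that the working rule is clear enough. Section 8.2 governs conduct, states a rule and is echoed throughout the protocol. Section 14 is a forecast, and it calls its window desired. A site following the protocol would use 6 to 12 weeks. Much of this stands: Section 14 is the outlier, and the remedy belongs there. But Section 14 does not stop at a forecast, because its next sentence excludes these subjects. Nor does it help to say that Section 8.2 governs sampling and Section 14 governs analysis. The 12 to 16 week rest would still be unscheduled, and subjects meeting the stated minimum would give repeated samples only to be left out of the main analyses. Permission to analyze the excluded data separately does not settle who is in the main set.

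The consequences are also modest. Section 13 fits curves to each subject individually, so dropping one subject leaves every other curve unchanged. It plans no tests or confidence intervals, and says that, strictly, Period 1 enters no statistical analysis, although it does yield birth and disappearance rates. That stands.

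Three stronger readings are tempting, and the documents do not support them.

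- A reader might infer that the evaluable count could fall well below 18, by taking the 20% as the share resting under 6 weeks and then removing the 6 to 12 week group as well. Section 14 ties the 20% expressly to 12 to 16 weeks, so that reading contradicts its text.
- A reader might infer that the results could be steered by choosing the rule after seeing the curves. With per-subject fits and no formal inference, this reaches little beyond descriptive summaries and the tertiary comparisons.
- A reader might infer that exclusion criterion 2, which speaks of a delay of two months or more, is wrong as well. Its wording is open-ended and already covers the full delay. Replacing it with a 10 to 16 week figure would leave out the approved short rest in Section 8.2.

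**Conclusion.** The conflict is real, and no other section resolves it. As written, Section 14 would drop subjects who rested 6 to under 12 weeks on schedule, and its second 20% loss refers to a window that the protocol does not schedule. Taking that 20% as the share not reaching 12 weeks, the Section 8.2 rule gives 18 to 24 evaluable of 30, which is equal to or better than planned. This rests on three assumptions: the plan's additive losses, the 12-week lower bound as Section 14's cut-off, and the treatment of anyone who starts before 12 weeks as unable to wait. The effect is on membership of the main descriptive analysis and on the evaluable count that drives accrual. No error rate is involved. It should be fixed because it concerns a stated analysis-set rule for the primary objective and the correction is short.

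**What to change.** In Section 14, replace the 12 to 16 week rule with: *Subjects with less than 6 weeks between the end of labeling and the first PCI-32765 dose, and without study PI approval, will be excluded from the Period 1 and 2 analyses.* Add that any such approval is recorded before that subject's kinetic data are seen. Restate the second 20% loss, and with it the 18 of 30, against this rule. The documents give no rate for failing a 6-week minimum, so the sponsor would need to justify a figure or show a range.

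This costs one rule, one sentence on approvals and one loss figure. It adds no visits, samples or subjects.

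If at least 12 weeks of rest is truly needed, the change belongs in Section 8.2 instead. It must then be carried through Sections 8.9 and 10.0 and footnotes k, l and q, with visits added after Day 112 if rests may exceed 12 weeks. That is more than a wording change.

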## 2.4 Results in CLL

[name] and his colleagues at The Feinstein Institute for Medical Research of the North Shore - LIJ Health System have used the technique to successfully determine the kinetics of CLL cells in subjects. Nineteen subjects imbibed heavy water for 12 weeks, and blood was collected at multiple time points during and after heavy water ingestion. CLL cells were isolated and analyzed for GC/MS analysis. The kinetic studies revealed significantly higher levels of proliferation than expected, with subject to subject variation in CLL birth rates ranging from 0.1% – 1.7%/day. Those subjects with a more rapid rate (defined as > 0.35%/day) were more likely to have progressive/active disease (8/10) than subjects with lower birth rates (< 0.35%/day) (1/9), as defined by the NCI-Working Group criteria.

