**4.0 Objectives**

The primary objective is to assess the impact of the Bruton's tyrosine kinase (Btk) inhibitor PCI-32765 on leukemia cell trafficking and death using heavy water ( $^2\text{H}_2\text{O}$ ) labeling of newly-born malignant cells in subjects with Chronic Lymphocytic Leukemia (CLL) and Small Lymphocytic Lymphoma (SLL).

The secondary objective is to determine the percent of recently born versus older leukemia cells mobilized into the blood by PCI-32765 treatment.

The tertiary objective is to compare the kinetic biomarker measurements in CLL subjects to other established prognostic tests and response to therapy with PCI-32765.

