## **8.0 Treatment Plan**

### **8.1 Heavy Water Protocol: Labeling phase.**

After enrollment and a baseline blood draw (60ml), subjects will start to consume heavy water ( $^2\text{H}_2\text{O}$ ). Subjects will be given 50 mL of 70%  $^2\text{H}_2\text{O}$  3 times a day for the first 5 days followed by 60ml daily for a total of 4 weeks (labeling phase). Lightheadedness or dizziness may occur for some subjects (~15%) with the initial doses; therefore subjects will be given their first dose in clinic and asked to avoid driving or performing potentially hazardous activities for one hour. If such symptoms occur, they usually abate within 2-3 hours. Subjects will then be given individual doses of  $^2\text{H}_2\text{O}$  to consume at home; after the 5-day loading period, a 60 mL maintenance dose of  $^2\text{H}_2\text{O}$  will be drunk at bedtime to obviate any problems with dizziness. Compliance with  $^2\text{H}_2\text{O}$  ingestion will be documented using a heavy water ingestion diary (intake logs). Unused  $^2\text{H}_2\text{O}$  will be returned for disposal.

Subjects will be seen at day 1 (+/- 3 days), day 14 (+/- 3 days), and day 28 (+/- 3 days) after beginning  $^2\text{H}_2\text{O}$  ingestion for follow-up visits with clinical and laboratory assessment, which will include determining if there have been any problems with  $^2\text{H}_2\text{O}$  ingestion, analysis and discussion of intake logs, and blood sampling (60ml) for CLL cell kinetic measurements (heavy water testing).

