### 13.0 Statistical Considerations

The primary objectives of the statistical analysis will be (1) to demonstrate that there is a population of CLL cells that do not leave or take sanctuary outside of the peripheral blood system in solid lymphoid tissues, (2) to describe the longitudinal pattern in observed labeled cells and (3) to estimate rates of cell death.

For purposes of statistical analysis, the experiment will be divided into two periods (with each period, itself, being divided into two subperiods): Period 1 corresponds to the non-interventional period when heavy water is consumed for 4 weeks (Period 1a) and then discontinued (Period 1b) so that a CLL cell disappearance rate can be tracked over time.

Period 2 corresponds to the interventional period when Btk inhibitor (PCI-32765) is administered to subjects. Assuming that the observed percentage of labeled cells (LC) reaches a peak at some point in time,  $T$ , then Period 2a is defined as the “pre-peak” sub-period (i.e., all times  $t \leq T$ ) and Period 2b is the “post-peak” sub-period ( $t > T$ ).

[figure not shown]
[figure not shown]
Strictly speaking, Period 1 does not enter into any statistical analysis, as it only serves to provide labeling for the cells that allegedly remain and return and are retained in solid tissues. However, Period 1 will permit definition of CLL cell birth rate and disappearance rate (death and permanent return to solid tissue from blood).

An important part of the statistical analysis in Period 2 is characterization of the pattern of LC over time. Patterns will be analyzed both visually and using more formal statistical methods in an exploratory manner. First, the pattern will be smoothed using a cubic spline interpolation (SAS Graph, SAS Institute, Cary, NC). This will facilitate the determination of shape and numbers and patterns of peaks by eliminating “noise” in the data. Second, based on the patterns observed after smoothing, the data will be fit to candidate regression models (e.g., parabolas, mixtures of parabolas, piecewise curves, etc.) and the best fitting model will be identified using common statistical methods such as  $R^2$ , Akaike’s information, etc. All curves will be fit on individual subjects, thereby permitting subjects to vary in the pattern of their LC response curves.

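### Section 14 drops subjects who cannot delay treatment from Period 1 as well as Period 2, which is broader than a short rest justifies and probably removes faster-growing disease from the birth-rate results

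*Combined protocol and SAP*

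**What the plan says.** Section 14 gives the expected yield: "The proposed sample size is 30 subjects of which it is expected that 18 (approximately 60%) will be evaluable". It names two groups that account for the loss. For the first, "it is expected that about 20% of subjects will exhibit a delayed release of labeled cells into the circulation in Period 1". For the second, "it is anticipated that 20% of subjects will not be able to delay treatment for the desired 12-16 weeks post-labeling". Of the second group it says: "These subjects will also be excluded from both the Period 1 and 2 analyses, but their data may be analyzed and used separately".

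Section 13 divides Period 1 into the 4-week labeling phase (1a) and the rest after heavy water stops (1b), and states that "Period 1 will permit definition of CLL cell birth rate and disappearance rate". Section 8.1 plans labeling-phase visits with kinetic blood samples at days 1, 14 and 28. Section 8.2 adds a draw every 2 weeks during the rest, until PCI-32765 starts.

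The tertiary objective in Section 4.0 is to "compare the kinetic biomarker measurements in CLL subjects to other established prognostic tests and response to therapy". Section 2.4 reports that, in an earlier heavy-water study of 19 subjects, those above 0.35%/day "were more likely to have progressive/active disease (8/10) than subjects with lower birth rates" (1/9).

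**The concern.** The reason for excluding the second group is that the rest before treatment was too short. That is a sound reason for leaving them out of any analysis that needs a long rest. It is not a reason for leaving them out of a birth-rate summary, because label uptake took place before the rest began. As written, one rule covers quantities that a short rest affects differently.

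The exclusion is also unlikely to be neutral. Subjects who cannot wait plausibly include those whose disease is advancing, and Section 2.4 associates active disease with a high birth rate. The rule may therefore select on the quantity being described. At stake are the descriptive birth-rate results, which could read too low, and the birth-rate part of the tertiary comparison, where losing the fast end would narrow the range and tend to weaken any association. Separate analysis of these subjects is allowed, but it is optional and unspecified.

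**Working it through.** **1. The plan's own figure.** Inputs from Section 14: 30 enrolled, 20% lost to delayed release, 20% lost to inability to delay.
- Non-overlapping losses: 30 × (1 − 0.20 − 0.20) = 18, as stated.
- Independent losses: 30 × 0.8 × 0.8 = 19.2, close to it.

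**2. What a short rest affects.**

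| Quantity | Data needed | Effect of a short rest |
|---|---|---|
| Label uptake (Period 1a) | Draws at days 1, 14, 28 | None; completed beforehand |
| Disappearance rate (Period 1b) | Two-weekly rest draws | Truncated |
| Labeled-cell pattern on treatment (Period 2) | Adequate prior rest, then on-treatment draws | Compromised |

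Section 14 measures the missed delay from the end of labeling, so labeling is over for this group by definition. Section 8.2 applies its own washout rule only to later kinetic studies and names no exclusion from Period 1.

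**3. Numbers for birth rate.** Dropping only the delayed-release group leaves 30 × 0.80 = 24. The current rule therefore removes 6 of 24 (25%). With the same between-subject spread, the standard error of a mean would be √(24/18) = 1.155 times as large, about 15% more. The 24 is a ceiling, because each restored subject must still have detectable labeled cells and usable draws.

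**4. Possible shift in the mean.** Let r be the mean birth rate of the 6 excluded subjects divided by that of the 18 retained. The mean of all 24 is (0.75 + 0.25r) times the retained mean, so the reported mean is too low by 1 − 1/(0.75 + 0.25r). The documents give no value for r; the values below are assumptions.

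| r | Reported mean too low by |
|---|---|
| 1 | 0% |
| 1.5 | 1 − 1/1.125 = 11% |
| 2 | 1 − 1/1.25 = 20% |
| 3 | 1 − 1/1.5 = 33% |

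If r were below 1, the sign would reverse.

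**5. Possible shift in the share above 0.35%/day.** In the earlier study 8 + 1 = 9 subjects had active disease, and 8 of those 9 (89%) were above the cut-off. Every subject here needs a treatment indication (Section 6.0, inclusion criterion 2), so suppose 89% of the 24 are above it: 24 × 8/9 = 21.3.
- If the 6 excluded are also 89% fast, the retained share is (21.3 − 5.3)/18 = 89%, a shift of 0.
- If all 6 are fast, it is (21.3 − 6)/18 = 85%, a shift of about 4 points.

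**The case against.** Several points on the other side stand.

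- A reader might infer that a short rest matters only to Period 2. It does not: Period 1b is the rest, and the disappearance rate is a Period 1 quantity that a short rest cuts directly.
- A reader might infer that labeling draws alone are enough for a birth rate. The documents do not say so. Section 13 assigns the birth rate to Period 1 as a whole, Section 8.2 mentions it alongside later samples, and the earlier study labeled for 12 weeks and sampled afterwards too.
- Section 14 does not say why subjects cannot wait. The 8/10 against 1/9 contrast separates active from non-active disease; it does not rank subjects who all need treatment. Exclusion criterion 2 also bars a lymphocyte doubling time under 3 months, so the fastest disease is partly screened out at entry.
- A reader might infer a large, known bias. For example, spreading birth rates log-uniformly over the quoted 0.1 to 1.7%/day and dropping the fastest fifth takes the mean from 1.6/ln 17 = 0.565 to 0.381%/day, a 32% fall. The documents do not support that. The range comes from a cohort mixing active and non-active disease, and nothing shows that inability to wait picks out exactly the fastest subjects.
- Section 13 says Period 1 is strictly outside the statistical analysis, plans no formal inference, fits curves to individual subjects and specifies no pooled mean birth rate. Birth rate is not named in the primary or secondary objective.

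These points limit the size and reach of the problem. They do not remove it. Section 14 itself refers to Period 1 analyses, Section 13 gives Period 1 the birth rate, and an optional separate analysis leaves the main birth-rate summary without these subjects.

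**Conclusion.** The concern holds in a limited form. The Period 1 exclusion is wider than its reason, costs up to 6 of 24 subjects for birth rate, and probably leans against faster-growing disease. That direction is an inference from Section 2.4 and is not stated in the plan.

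The size is unknown. The 0% to 33% range rests on an assumed ratio of 1 to 3, and the 0 to 4 point shift rests on nearly all enrolled subjects already being above 0.35%/day. Only the descriptive birth-rate results and the tertiary comparison are exposed. Because the correction uses samples already planned, it is worth making even in an exploratory pilot.

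**What to change.** Amend Section 14 so that subjects unable to delay treatment are excluded from the Period 2 analysis and, where the rest is too short to fit a slope, from the disappearance-rate analysis, and from nothing else. Keep them in the birth-rate summary and the birth-rate part of the tertiary objective whenever labeled cells are detectable and the available pre-dose draws support an estimate. Cut their data at first PCI-32765 dose for this purpose. Report birth rates with and without them, so that any difference can be seen.

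Section 14's definition of an evaluable patient requires adherence through labeling, rest and treatment, so the birth-rate set needs its own short definition.

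The delay of 12-16 weeks after labeling in Section 14 and the 6-12 week rest in Section 8.2, with its 6-week threshold and investigator-approved exceptions, must also be reconciled. Read literally, a rest of 6 to under 12 weeks satisfies Section 8.2 but falls short of Section 14, so the excluded group could exceed 20%.

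The cost is a sentence or two of text; no new samples or assays are needed. The small downside is less precise birth-rate estimates in subjects with few rest-phase draws.
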